identified when uploaded. Next, up to 3 skin swabs will be performed on each arm in a region of eczematous skin and non-lesional skin, for a total of up to 12 swabs. For the skin swabs, one culture swab and one to two DNA swabs will be taken from the eczematous skin from each arm, and one culture swab and one to two DNA swabs will be taken from the non-lesional skin on each upper inner arm for a total of up to twelve (12) swabs. After swabbing, the swabs are placed into either an empty Eppendorf tube (if analyzing the DNA of the bacteria present on the skin surface) or into a liquid medium such as tryptic soy broth (if analyzing the amount of bacteria present on the swabbed skin surface). These swabs will be analyzed in the lab to determine how many and what type of bacteria are present. The AMT cream or vehicle cream will then be applied to both arms by the gloved hands of a study coordinator. The moisturizers will be provided by [name] laboratory and will be in identical containers labeled either A or B. Neither the study coordinator nor the subject will know which cream is in which container. Container A or B will contain either Cetaphil alone or Cetaphil plus colonies of the subject's endogenous AMP-producing Staph grown in the lab from the subject's screening swab. A thin coat of cream A or B will be applied to both arms (excluding hand) in order to demonstrate proper application. Up to twelve (12) skin swabs will then be performed on both arms in the areas of cream application on lesional and non-lesional skin, between 5 minutes to an hour after cream application, depending on the discretion of the investigator. Following the skin swabs, the Cetaphil alone or Cetaphil with AMP-producing Staph will be reapplied onto the subjects' arms as previously described. The subject will be instructed to withhold use of any topical or oral AD medications until after their last in-clinic follow-up visit (Visit 8). The subject will be provided with aliquots of either the transplant or vehicle creams, enough for at least 4 days of application. Subjects will be instructed to apply the cream twice a day for the next 4 days, and will be instructed to apply the provided cream from one aliquot per arm. To minimize cross contamination, we will instruct subjects to wear long sleeve clothes and change into clean clothes every day. All creams should be stored at room temperature. Subjects will be reminded to use Dove soap provided to them, whenever they shower, but to avoid the upper extremities, until after their last in-clinic visit on Day 11 is complete. Subjects will be instructed to continue their daily skin care routine, and discouraged from using antibacterial soaps and swimming in the ocean or pool until their last in-clinic follow-up visit. They will also be instructed that if these events occur, to please notify the study staff at their next visit. At the end of the visit, subjects will be given an instruction sheet and a subject diary to assess for cream application appliance. They will be asked to bring the diary pages to their Follow-up Visit 4. This will conclude the treatment visit. We expect this visit to take approximately 20 minutes.

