Visit 7 (Day 9 +/- 7): Subjects will be asked to return to the clinic for Visit 7 for follow-up. Subjects will be asked to refrain from bathing, exercising, or showering starting at 12:01am of Visit 7. Vital signs will be taken. Any adverse events since the last visit will be recorded. A brief exam of the skin on subjects' arms will be performed. For subjects with AD, the severity of AD on each arm will be graded using the localized SCORAD, modified EASI, and global SCORAD and EASI grading. Subjects will also be asked to grade their pruritus on a scale of 1-10, with 10 being the worst pruritus of their life. Digital photographs of the lesional skin on both arms will be taken. Next, one culture swab and one to two DNA swabs will be taken from the eczematous skin from each arm, and one culture swab and one to two DNA swabs will be taken from the non-lesional skin on the upper inner arm for a total of up to twelve (12) swabs. We expect this visit to take approximately 15 minutes.

Visit 8 (Day 11 +/- 7): Subjects will be asked to return to the clinic for Visit 8 for follow-up. Subjects will be asked to refrain from bathing, exercising, or showering starting at 12:01am of Visit 8. Vital signs will be taken. Any adverse events since the last visit will be recorded. A brief exam of the skin on subjects' arms will be performed. For subjects with AD, the severity of AD on each arm will be graded using the modified EASI, and global SCORAD and EASI grading. Subjects will also be asked to grade their pruritus on a scale of 1-10, with 10 being the worst pruritus of their life. Digital photographs of the lesional skin on both arms will be taken. Next, one culture swab and one to two DNA swabs will be taken from the eczematous skin from each arm, and one culture swab and one to two DNA swabs will be taken from the non-lesional skin on the upper inner arm for a total of up to twelve (12) swabs. At the conclusion of this visit, subjects may resume prohibited medications, as needed, and may use their choice of soap and emollient. We expect this visit to take approximately 15 minutes.

Visit 9, Phone 2 (Day 38 +/- 7 days)

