If the subject calls to report a possible infection during a time when the clinic is closed, the subject will be directed to the resident on call or closest urgent care facility for further management.

2. Risk of medication withdrawal: Discontinuation of a person's AD medication prior to participating in this study and also the prohibition of using AD medications for periods of time during this study may result in worsening or temporary flaring of the patient's AD.

As listed in the inclusion/exclusion criteria (section 10), subjects with severe AD who may have difficulty tolerating periods without medication use will be excluded from participating. Subjects enrolled in the study will be able to use over-the-counter moisturizers as needed. Moisturizers play a role in helping to prevent and control AD flares, and therefore may be of use to subjects whose AD is worsening. The time during which subjects are unable to treat their AD during the study will be limited to the 7-days prior to each screening and treatment/follow-up visit for topical medications, and 28-days prior to each screening and treatment/follow-up visit for oral medications. If for some reason severe worsening of AD occurs during a time in the study that subjects are not permitted to use their medication, the subject will be permitted to use their medication, however the upcoming visit must be rescheduled so that the required 7-day and 28-day wash-out periods before each screening and treatment/follow-up visits are observed. Since the visit dates for the study are relatively flexible (the only real time-dependent visit is the Follow-up Visit, which must occur approximately 24 hours after the Treatment Visit), rescheduling subject visits should not affect study results. AD itself is a chronic condition characterized by periods of flaring and remission. Any worsening of the subject's AD would constitute a disease flare that should be correctable with the use of medications. Flares of AD do not result in permanent deterioration of the subject's

condition. Finally, topical medication discontinuation must only be observed on the subject's bilateral arms since this is the site being studied during the trial. Subjects may treat the AD on all other body surfaces with topical medications throughout the study.

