13.2.2 Secondary Endpoint(s)/Outcome(s)

Secondary Lesional AD skin:

1. The abundance of the AMT bacterial strains on lesional skin at baseline and after 1 week BID application of AMT.
2. The quantity of transplanted bacteria on lesional skin after stopping AMT cream 1 day, 2 days, and 4 days after last application.
3. The change in abundance of *Staph aureus* on lesional skin from baseline to 1 day, 2 days, and 4 days after stopping AMT.
4. Change in clinical assessments, including SCORAD, modified EASI, and EASI after 1 week BID application of AMT.
5. Identify lesional skin microbiome by DNA sequencing from baseline and after 1 week BID application of AMT.
6. Evaluate the lesional skin microbiome transcriptome by RNA-sequencing analysis from baseline and after 1 week BID application of AMT.

Secondary Non-lesional skin:

1. The abundance of *Staph aureus* at baseline and after 1 week BID application of AMT on non-lesional skin.
2. The abundance of AMT bacterial strains on non-lesional skin at baseline and after 1 week BID application of AMT.
3. The quantity of transplanted bacteria on non-lesional skin after stopping AMT cream 1 day, 2 days, and 4 days after last application.
4. The change in abundance of *Staph aureus* on non-lesional skin from baseline to 1 day, 2 days, and 4 days after stopping AMT.
5. Identify non-lesional skin microbiome by DNA sequencing from baseline and after 1 week BID application of AMT.
6. Evaluate the non-lesional skin microbiome transcriptome by RNA-sequencing analysis from baseline and after 1 week BID application of AMT.

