13.4.4 Analyses of Secondary and Other Endpoint(s)/Outcome(s)

Secondary Endpoints, Lesional AD skin:

1. The abundance of the AMT bacterial strains on lesional skin at baseline and after 1 week BID application of AMT.
 - a. The abundance of live *CoNS* species on lesional skin will be compared from baseline (day 28) to Day 35 after 1 week BID application of AMT cream versus placebo. This will be calculated using a two-tailed t-test for independent samples with type II error rate of 0.2 and type I error rate of 0.05.
2. The quantity of transplanted bacteria on lesional skin after stopping AMT cream 1 day, 2 days, and 4 days after last application.
 - a. Live antimicrobial *Staph* species will be measured on lesional skin at baseline (day 28), Day 35 (after 7 days of cream application), Day 36, Day 37, and Day 39 in order to evaluate the abundance of the antimicrobial *CoNS* species that remains after

stopping cream application. In order to take into account the variance of the abundance of antimicrobial *CoNS* species found on each subject's skin at baseline, we will perform CFU counts at each time point (Day 28, 35, 36, 37, and 38) and evaluate the percentage of antimicrobial species present at each time point. The percentage of antimicrobial species present at each time point will be compared between the AMT cream arm and placebo arm using a two-tailed t-test for independent samples with type II error rate of 0.2 and type I error rate of 0.05.

3. The change in abundance of *Staph aureus* on lesional skin from baseline to 1 day, 2 days, and 4 days after stopping AMT.
 - a. The abundance of live *Staph aureus* on lesional skin will be evaluated using CFU counting at baseline, 1 hour, and 4 hours after initial application of AMT or placebo cream, and after 4 and 7 days of cream application. At each time point, we will compare the AMT cream and placebo arms by using a two-tailed t-test for independent samples with a type I error rate of 0.05 and type II error rate of 0.2.
4. Change in clinical assessments, including SCORAD, modified EASI, and EASI after 1 week BID application of AMT.
 - a. A modified EASI, global SCORAD and EASI score will be assessed at baseline 1 week BID application of AMT cream or vehicle cream. Using percentage of improvement of these scores, we will compare percent reduction of AD severity between AMT cream and placebo cream using a two-tailed t-test with type I error rate of 0.05.

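### The cream is applied only to the arms, but no score in the clinical secondary analysis is clearly confined to the arms; localized SCORAD, collected at Day 0 and Day 7, is left out of it

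*Combined protocol and SAP*

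**What the plan says.** **Treated area.** At the Treatment visit (section 8.3, Visit 3), "A thin coat of cream A or B will be applied to both arms (excluding hand"). Section 6.2 gives the same area for home dosing.

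**Endpoint.** Section 13.2.2, lesional skin item 4: "Change in clinical assessments, including SCORAD, modified EASI, and EASI after 1 week BID application of AMT".

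**Analysis.** Section 13.4.4, lesional skin item 4: "A modified EASI, global SCORAD and EASI score will be assessed at baseline 1 week BID application of AMT cream or vehicle cream". The comparison is of "percent reduction of AD severity between AMT cream and placebo cream using a two-tailed t-test with type I error rate of 0.05".

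**Scores collected.** Section 8.3 lists localized SCORAD beside modified EASI, EASI and SCORAD at Visit 3 (Day 0) and Visit 5 (Day 7). The synopsis, the objectives in section 2, section 13.2.2 and section 13.4.4 do not name it.

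**Topical AD medication during the study.** Section 8.3, Visit 3: "The subject will be instructed to withhold use of any topical or oral AD medications until after their last in-clinic follow-up visit (Visit 8"). Section 12.2, under the risk of medication withdrawal: "Subjects may treat the AD on all other body surfaces with topical medications throughout the study".

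**The concern.** The clinical question is whether the cream improves the skin it is applied to. A score that covers the whole body answers this only indirectly, because most of what it can register lies where no cream goes. If the analysed scores are whole-body, a real effect on the arms would look smaller than it is, in a trial of 18 against 9 subjects.

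The two medication rules add to this. If subjects may treat off-arm skin with topical drugs, a whole-body score also moves with that treatment. Section 13.4 has no step that takes such use into account. Meanwhile the one score labelled as localized is collected at both ends of the treatment week and not analysed.

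**Working it through.** The plan states no figure on this point, so there is none to reproduce. The check is mainly a comparison of sections.

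**1. Which analysed score is tied to treated skin?**

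| Score | Endpoint (13.2.2) and analysis (13.4.4) | Body area stated |
|---|---|---|
| SCORAD | Yes | Called global in 13.4.4 and in 8.3, Visits 5 to 8 |
| EASI | Yes | Called global in 8.3, Visits 3 and 4 |
| Modified EASI | Yes | Listed apart from global EASI; never defined |
| Localized SCORAD | No | By its name, local; collected at screening and Visits 3 to 7 |

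The visit text complicates this. At Visits 3 and 4 it says that all the listed scales, including the global ones, rate lesional skin on both arms. From Visit 5 on it speaks of severity on each arm. The scoring area is therefore unclear, and no analysed score can be shown to be confined to the arms.

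**2. What follows if a global score is whole-body?** Treat the score as additive over body areas. Let w be the arms' share of the baseline score, A the percent improvement on the arms and B the percent improvement elsewhere. Then

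total percent improvement = w × A + (1 − w) × B.

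With the same B in both groups, the between-group difference in the total is w times the difference on the arms. The documents do not give w, so the following only illustrates the formula over an assumed range. It is not an estimate for this trial.

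- A 50% arm improvement with B = 0 appears as 10%, 15%, 25% and 40% for w = 0.2, 0.3, 0.5 and 0.8.
- With 18 against 9 subjects and a two-sided 0.05 t-test, 80% power needs a standardized difference of 1.19. If the arms show exactly that, and the SD of percent change is the same for both scores (a further assumption), the non-centrality is w × 1.19 × √(18 × 9 / 27) = 2.91w with 25 degrees of freedom. Power is then about 0.09, 0.13, 0.29 and 0.61 for the same values of w.

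**3. Which topical rule applies off the arms?** The section 8.3 instruction has no body-site limit and runs to the end of Visit 8. Section 12.2 permits topical drugs everywhere except the arms for the whole study. Exclusion 1 in section 4.3 and item 1 in section 7.2 limit the ban to the arms, but they cover only the week before the Treatment visit and so do not settle the on-study rule. Sections 8.3 and 12.2 contradict each other. Under section 12.2, B varies between subjects for reasons unrelated to the cream.

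**4. Is off-arm use recorded?** Yes. Table 1 schedules concomitant medications at Visits 3 to 8. No analysis in section 13.4 uses them.

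**The case against.** The strongest reply is that modified EASI may already be the arm-level score. It is in both the endpoint and the analysis and is listed separately from global EASI. If it is arm-level, treated skin is analysed at Day 7. The visit text also places the grading on the arms, and the endpoint sits under lesional skin. This reply stands to the extent that whole-body scoring is not proven. It does not remove the point, because modified EASI has no definition and the global label conflicts with the arm wording.

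A reader might infer three stronger things that the documents do not support.

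- *That the comparison cannot show a benefit on treated skin.* This would require modified EASI not to be arm-level, which the text does not establish.
- *That off-arm topical use could cancel or reverse a benefit.* Suppose the arms improve by 30% on AMT, and 2 of 9 placebo subjects but no AMT subject halve their off-arm disease. The gains in the total are 0.30w and (1 − w) × 0.5 × 2/9 = (1 − w)/9. These are equal at w = 1/3.7 = 0.27. At w = 0.2 they are 6.0% and 8.9%; at w = 0.4 they are 12.0% and 6.7%. Cancellation needs a small arm share and use in one group only. Allocation is randomized and blinded, and equal use (4 of 18 and 2 of 9) adds no expected difference. Chance imbalance is possible, but nothing in the documents gives its size.
- *That the lack of localized SCORAD at Visit 8 is a gap.* There severity is "graded using the modified EASI, and global SCORAD and EASI grading", but clinical change is defined after one week of application, and localized SCORAD is collected at that visit.

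**Conclusion.** The point holds in a limited form. The treated area is the arms. Two of the three analysed scores are named as global, the third is undefined, and the score labelled as localized is collected at Day 0 and Day 7 without being analysed. Sections 8.3 and 12.2 contradict each other on topical AD medication off the arms.

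Dilution follows only if the global scores are in fact whole-body, and its size depends on the arms' share of the score, which the documents do not give. No figure for this trial can be stated. The primary *S. aureus* endpoint is not affected. This is an improvement to one secondary endpoint at almost no cost, not a flaw that invalidates the clinical comparison.

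**What to change.** - In sections 13.2.2 and 13.4.4, lesional skin item 4, add the change in localized SCORAD from Day 0 to Day 7 as an analysed arm-level clinical endpoint. State how the two arms are combined into one value per subject. Carry the wording into the synopsis and section 2.
- Define modified EASI, and state the body area covered by each of the four scores.
- State that global SCORAD and EASI will be interpreted in light of off-arm topical use, taken from the concomitant medication records. They can stay in the analysis.
- Reconcile section 8.3 (Visit 3) with section 12.2 on topical AD medication off the arms. Which rule applies is for the investigators to decide.

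The cost is protocol and SAP wording plus one more t-test on data already scheduled. No visit or assessment is added. The number of clinical scores tested at 0.05 rises from three to four, which the report should make plain.

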12.2.1 Adverse Event (AE)

Reporting Procedures for All Adverse Events

The investigator is responsible for ensuring that all adverse events are properly recorded in the subjects' records. After signing of the informed consent form, all adverse events observed by the investigator or reported by the subject (whether or not attributed to investigational product), will be recorded in the case report form.

The following attributes must be assigned by the investigator: description; dates of onset and resolution; severity; assessment of relatedness to investigational product, and action taken. The investigator may need to provide follow-up information, medical records, and extracts from medical records.

UCSD IRB

Unanticipated problems involving risk to participants or others (UPRs) are defined as any problem or event, which in the opinion of the Principal Investigator was: 1) unanticipated, 2) serious, AND 3) at least possibly related to the research procedures. If the event meets all 3 criteria for a UPR, it should be reported to the UCSD IRB within 10 working days. The following are events that meet the definition of UPR:

1. Any serious event (including injuries, side effects, deaths or other problems) that in the opinion of the Principal Investigator was unanticipated, involved risk to subjects or others, and was at least possibly related to the research procedures.
2. Any serious accidental or unintentional change to the IRB-approved protocol that alters the level of risk.
3. Any deviation from the protocol taken without prior IRB review to eliminate apparent immediate hazard to a research subject.
4. Any new information (e.g. publication, safety monitoring report, updated safety report), interim result or other finding that indicates an unexpected change to the risk/benefit ratio of the research.
5. Any breach in confidentiality that may involve risk to the subject or others.

6. Any complaint of a subject that indicates an unanticipated risk or that cannot be resolved by the Principal Investigator.

A brief summary of all UPRs as well as a brief summary of all adverse events will be submitted with the continuing review.

Food and Drug Administration

The Principal Investigator will notify the FDA directly in a written IND safety report of any adverse experience associated with the use of the drug that is both serious and unexpected or any finding from tests in laboratory animals that suggests a significant risk for human subjects including reports of mutagenicity, teratogenicity, or carcinogenicity. Each notification will be made as soon as possible and in no event later than 15 calendar days after the initial receipt of the information. Each written notification will be submitted on FDA Form 3500A. The Principal Investigator will also notify FDA by telephone or by facsimile transmission of any unexpected fatal or life-threatening experience associated with the use of the drug as soon as possible but in no event later than 7 calendar days after initial receipt of the information.

On an annual basis as part of the update to the study IND, the Principal Investigator will submit to the FDA directly a narrative or tabular summary showing the following:

- The most frequent and most serious adverse experiences by body system
- A summary of all IND safety reports submitted during the past year
- A list of subjects who died during participation in the investigation, with the cause of death for each subject
- A list of subjects who dropped out during the course of the investigation in association with any adverse experience, whether or not thought to be drug related

12.3 Grading and Attribution of Adverse Events

12.3.1 Grading Criteria

Clinical investigators will “grade” the severity of all AEs using the following scale; the results will be reported on the SAE form, if necessary.

1 = MILD – aware of sign or symptom, but easily tolerated

2 = MODERATE – discomfort enough to cause interference with usual activity

3 = SEVERE – incapacitating with inability to work or do usual activity

4 = LIFE-THREATENING – refers to an event in which the patient was, in the view of the investigator, at risk of death at the time of the event. It does not refer to an event which hypothetically might have caused death if it were more severe.

5 = FATAL

